5. The link will take you to the Project Summary page for the project. Follow the PI instructions for items #4 and #5 above.

If you are a contact (member of research team) and you wish to access minutes or approved materials:

1. Login to the regular myIRB website as yourself.
2. Scroll to the listing of "Projects" at the bottom of your Inbox page.
3. Change the filter for the Project to show projects where you are a research team member and click "Go" on the filter.
4. Click on the IRB number for the approved project.
5. The link will take you to the Project Summary page for the project. Follow the PI instructions for items #4 and #5 above.

E1 Overview or Design Summary

ED patients will be approached for informed consent if they meet selection criteria. Patients who consent to be in the trial will be randomized to either morphine (0.1mg/kg maximum dose of 10 mg) or ketamine (0.4 mg/kg, maximum dose of 40 mg). During the consent process, patients can be pretreated for pain with fentanyl IV up to 100mcg. Patients will not be given their assigned pain medication until at least thirty minutes after administration of any fentanyl to avoid overlapping effect of fentanyl with ketamine or morphine.

~~ED patients will be approached for informed consent if they meet selection criteria. Patients who consent to be in the trial will be randomized to either morphine (0.1mg/kg maximum dose of 10 mg) or ketamine (0.4 mg/kg, maximum dose of 40 mg).~~

PHARMACY NOTIFICATION

The research pharmacy will be notified of a potential study participant so they can prepare to randomize the participant using a random number generator. Odd numbered participants will receive ketamine and even numbered participants will receive morphine. Participants in the low dose ketamine arm will receive 0.4 mg/kg IV of ketamine (40 mg maximum). Participants in the opioid arm will receive 0.1 mg/kg of morphine up to 10 mg.

PHARMACY FORMULATION

Upon the completion of consent, the pharmacy will be notified to draw up the appropriate medication and send the medication to the Emergency Department. The study medication will be in identical appearing unmarked syringes, so that neither the study team nor the study subject will know which medication is being administered.

VITAL SIGN COLLECTION

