Adverse events and serious adverse events will be noted on the data form and treated by the study physician or the primary treating physician as medically indicated.

E2 Subject Selection and Withdrawal

2.a Inclusion Criteria

Patients over the age of 18 presenting with long-bone fractures are eligible for enrollment. Eligible long-bone fractures include fractures of the shaft of the humerus, radius, ulna, femur, tibia, and fibula.

2.b Exclusion Criteria

Patients with injuries older than 24 hours will be excluded. Patients with avulsion fractures will be excluded. Patients with a history of substance abuse, chronic opioid dependence, pregnancy, intoxication, allergy to ketamine or opioids, and those that cannot consent (e.g. active mental disease preventing them from having capacity to consent) will be excluded. Any patients with hemodynamic instability defined as systolic blood pressure > 180 mmHg or < 100 mmHg, heart rate > 130 bpm, respirations < 10 rpm, or oxygen saturations on room air < 90% shall also be excluded. In addition, any patient that received a narcotic analgesic aside from fentanyl within the last 2 hours will be excluded.

2.c Study Termination

Subjects can terminate their participation in the study at any time. The alternative to continuing in the study is to have the pain treated by emergency physicians and staff as per usual care. The study physician may terminate the study prior to the specified endpoint when deemed medically prudent to do so.

2.d Ethical Considerations

Current research has investigated the effectiveness of ketamine as an analgesic in the Emergency Department. Much of that research is observational which limits the conclusions that can be drawn. While ketamine's mechanism of action would be consistent with an agent that can result in analgesia, we would like to conduct a randomized, blinded trial to determine if ketamine is as effective as an analgesic as morphine. We believe given the pharmacologic properties of ketamine, and prior published research, that ketamine is an effective analgesic so this research is important and ethical. All data will be collected by trained research staff and kept in a locked office to minimize the chance of lost data.

2.e Subject Recruitment Plans and Consent Process

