Patients who are identified as potential study participants will be approached by the research coordinators regarding informed consent. The purpose of the study, study procedures, and associated risks and benefits will be explained to the potential subject. Following this, subjects will have 10 minutes to review the consent form on their own and if they agree to participate in the study, the consent form will be completed.

2.f Randomization Method and Blinding

Randomization will occur in the research pharmacy using opaque, sealed envelopes. Twenty participants will be randomized into each arm. Participants in the LDK arm will receive 0.4 mg/kg IV of ketamine (40 mg maximum). Participants in the opioid arm will receive 0.1 mg/kg of morphine up to 10 mg. Medications will be prepared by the pharmacy and delivered to the treating nurse in identical syringes. Study drug will be blinded to the research team and the study participant.

2.g Risks and Benefits

Patient will be exposed to medical risks in both conditions. Patients exposed to morphine will be at risk for hypotension, respiratory depression, altered mental status and possible allergic reaction. Patients exposed to ketamine will be at risk for hypertension, dysphoria and in rare cases laryngospasm and emergence reaction. These side effects are well known by practitioners since both of these drugs are regularly given in the Emergency Department. Patients may also be at risk for inadequate pain control in either condition.

2.h Early Withdrawal of Subjects

Participants will be told they have the right to withdraw from the study at anytime for any reason. Participants will also be taken out of the study early if the physician, nurse or research coordinator decides that the participant is at risk for a life-threatening event. Since this study does not include any outpatient follow-up, we do not anticipate early withdrawal to be a problem.

2.i When and How to Withdraw Subjects

The research coordinator will continually monitor the participant, and the nurses and physicians will be able to remotely monitor the participant's vital signs at the telemetry station. If a life-threatening event is identified, the participant will be resuscitated as deemed appropriate by the physician caring for the participant.

2.j Data Collection and Follow-up for Withdrawn Subjects

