Due to the short duration of the study (60 minutes), we do not anticipate early withdrawal to be a problem. Participants who have inadequate pain relief and require rescue medication, or who have adverse events that require other treatment will have their data included, even if study personnel are unable to complete the follow-up VAS scores at 15, 30, or 60 minutes.

Study Drug

2.k Description

Ketamine is a dissociative agent that is thought to modulate pain by binding to NMDA receptors. Participants assigned to the ketamine arm will be given 0.4 mg/kg IV of ketamine (40 mg maximum).

Morphine is an opioid that acts on opioidergic receptors to modulate pain. Participants in the opioid arm will receive 0.1 mg/kg IV of morphine (10 mg maximum).

2.l Treatment Regimen

The study is designed to compare a one-time dose only. Therefore study medication administration will occur once following the baseline pain and vital sign assessment.

Assignment of Subjects to Treatment Groups

Participants will be assigned to either the ketamine arm or the morphine arm in the pharmacy by random number generator. Participants and all study personnel will be blinded to the assignment.

2.m Preparation and Administration of Study Drug

Once participants are in the process of being consented, the pharmacy will be notified to prepare the drug. The drug will then be sent to the Emergency Department for administration.

2.n Subject Compliance Monitoring

Participants will be given the drug intravenously by the emergency department staff nurse assigned to their care. The research coordinator will monitor the participant's vital signs, pain relief, and any side effects during the duration of the study. Since medication is only given one time, non-compliance will not be an issue.

Prior and Concomitant Therapy

Participants will be excluded from the study if they are found to be chronic users of either prescribed or illicit opioids or opiates.

2.o Packaging

Study drug will be packaged by the pharmacy in identical looking syringes so as to maintain blinding. This is a question for the pharmacy. I will email [name] about this.

2.p Blinding of Study Drug

As above

2.q Receiving, Storage, Dispensing and Return

The pharmacy will transport the study medication to the emergency department. If the patient withdraws from the study, the medication can be returned to the pharmacy.

F Study Procedures

F1 Screening for Eligibility

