Participants will be identified in the Emergency Department waiting room as a potential candidate for the study by nurses, physicians and the research coordinator on duty. If a long bone fracture is deemed highly likely or if a long bone fracture has been identified by X-ray, the injury occurred within 24 hours, and the patient is conscious and alert and hemodynamically stable they will be approached for consent.

F2 Schedule of Measurements

Participants will have vital signs collected immediately prior to administration of the medication to which they are assigned. Vital signs (heart rate, respiratory rate, blood pressure, and pulse oximetry) will be recorded every 5 minutes for the first 30 minutes following the administration of study drug, and then every 10 minutes until study

completion (60 minutes post medication administration). Pain severity will be assessed immediately prior to administration of medication via the VAS and at 15, 30 and 60 minutes following medication administration..

F3 Visit 1

The participant will only be treated on the first encounter in the Emergency Department.

F4 Visit 2 etc.

N/A

F5 Safety and Adverse Events

We will monitor and record for changes in vital signs including hypotension, hypertension, tachycardia, bradycardia, respiratory depression. We will also monitor for nausea and vomiting, laryngospasm, and emotional and psychological effects (emergence reactions).

5.a Safety and Compliance Monitoring

Participants will receive only one dose of study drug, thus compliance will not be an issue. Participants will be monitored continuously for alterations in vital signs, or any other adverse events during the entirety of the study.

5.b Medical Monitoring

Both of these medications are commonly used in the emergency department setting, and have a good safety record. Nonetheless, AEs, and SAEs may occur. Any adverse event directly linked to administration of either ketamine or morphine that results in permanent disability or death will result in the cessation of the entire study.

Further, after every 10 patients are enrolled, all AE's will be reviewed by an independent expert. If there is a high frequency of adverse events that cause great distress to participants or that results in many participants ending their participation, the study will be terminated.

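### Does approaching patients on a suspected fracture (F1) mean that E1 lets ineligible patients be randomised?

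*SAP*

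**What the plan says.** E1 (Overview or Design Summary) states: "ED patients will be approached for informed consent if they meet selection criteria". It continues: "Patients who consent to be in the trial will be randomized to either morphine" or ketamine.

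F1 (Screening for Eligibility) sets the condition for approach differently: "If a long bone fracture is deemed highly likely or if a long bone fracture has been identified by X-ray", together with injury within 24 hours, alertness and haemodynamic stability.

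The criteria themselves are in E2. Section 2.a says "Patients over the age of 18 presenting with long-bone fractures are eligible for enrollment" and "Eligible long-bone fractures include fractures of the shaft of the humerus, radius, ulna, femur, tibia, and fibula". Section 2.b includes "Patients with avulsion fractures will be excluded" among a longer list of exclusions.

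On timing, 2.m says "Once participants are in the process of being consented, the pharmacy will be notified to prepare the drug", whereas E1's pharmacy formulation paragraph places the request to draw up the drug at the end of consent. On size, 2.f says "Twenty participants will be randomized into each arm".

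**The concern.** E1 and F1 describe the same step, the approach for consent, under different conditions. F1 itself separates a probable fracture from one seen on X-ray, so under F1 the fracture need not be established when the patient is approached. E1 treats the selection criteria as already met at that point, and its next sentence makes consent the only stated condition for randomisation. The pharmacy steps that follow mention no return to 2.a or 2.b.

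Taken literally, a patient with a suspected fracture could consent, be randomised and be dosed, and then prove to have no fracture, a fracture outside the listed shafts, or an avulsion fracture. At stake would be how well the randomised group matches the population in 2.a. Precision could also suffer if such patients were later dropped from an already small trial.

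**Working it through.** There is no stated figure to reproduce. The check is mainly a comparison of the texts.

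1. **What 2.a and 2.b control.** 2.a defines who is eligible for enrolment, not who may be spoken to. 2.b says the listed patients are excluded and does not limit this to the moment of approach. Nothing in F1 waives either section.

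2. **What F1 is for.** It describes how staff spot a possible candidate in the waiting room. It names the fracture, the 24-hour limit, alertness and haemodynamic stability. It leaves out age, avulsion fracture, pregnancy, allergy, intoxication, substance abuse and recent narcotic use. A list that omits so many criteria cannot be the full eligibility test, so it reads as a pre-screen.

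3. **Whether other sections agree.** 2.e has coordinators approach people identified as potential participants. E1's own pharmacy notification paragraph also speaks of a potential participant. Both fit F1. Only the opening sentence of E1, in a section headed as an overview, says the criteria are already met at approach.

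4. **Whether eligibility facts are still gathered after approach.** The data form in E1 records history of drug abuse, prior narcotics, a description of the injury and earlier medication. The paragraph on prior and concomitant therapy excludes participants who turn out to be chronic opioid users. Neither is labelled an eligibility check before randomisation. Both show that the authors did not regard everything as settled at approach.

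5. **What an added sentence would achieve.** Suppose E1 said that only consenting patients recorded as meeting 2.a and 2.b are randomised. Those sections already require this. 2.a does not say how a fracture must be established, so a clinician who judges one highly likely could record 2.a as met. The same patient could then be randomised.

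6. **Size.** The SAP gives neither the number approached on suspicion nor the share later found ineligible. One participant is 1/20 = 5% of an arm and 1/40 = 2.5% of the trial, but that is true of any participant and says nothing about this issue. As an illustration only, let f be the share of randomised patients without a qualifying fracture, and suppose they are dropped from the analysis. Confidence intervals then widen by about 1/√(1 − f) − 1, ignoring the small change in the t quantile:

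| f (assumed) | Patients of 40 | Remaining | Widening |
|---|---|---|---|
| 5% | 2 | 38 | 2.6% |
| 10% | 4 | 36 | 5.4% |
| 20% | 8 | 32 | 11.8% |

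No value of f has support in the SAP. G1 bases the sample size on funding for a pilot, so no power target is missed.

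**The case for a change.** The best case for acting is that one of the two passages must be inexact. If F1 is only a pre-screen, E1 is wrong about what is settled at approach, and its randomisation sentence leans on a test not yet made. If E1 is right, F1 is too loose. No visible step between consent and assignment refers back to the criteria, and 2.m brings in the pharmacy while consent is still under way. A reworded sentence and a recorded check would cost little.

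The mismatch in wording stands: E1's first sentence is imprecise. So does the difference between E1 and 2.m on when the pharmacy is told to prepare the drug, although that concerns preparation and does not decide who is eligible. It also stands that the visible text gives no rule for a patient randomised and later found not to qualify.

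The step from there to ineligible patients being randomised does not stand. It rests on the silence of an overview sentence, against 2.a and 2.b, which apply in their own terms. The operational record of eligibility between consent and assignment is commonly left to the protocol, which is not at hand, and the SAP text breaks off in G2. Silence here therefore proves little. Nor is a check certain to be cheap: a form entry would change little, and one that waited for imaging would take a time the SAP does not give.

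**Conclusion.** The concern does not call for a change. It is a clerical slip: one overview sentence runs together finding a candidate and confirming eligibility, while 2.a, 2.b, 2.e and F1 keep them apart. A reader applying the plan would approach under F1 and enrol under 2.a and 2.b. Repeating those criteria in E1 would add no protection, because the standard for establishing a fracture would be as open as before.

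The consequence is confined to how clearly the randomised population is described. Its size cannot be derived from the SAP. No bias between arms is shown, since any such entry would precede the assignment and so could not depend on it.

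This rests on three assumptions: that staff apply 2.a and 2.b at enrolment as written; that assignment is random and concealed from those enrolling, as 2.f describes with sealed envelopes held in the pharmacy; and that nothing in the missing text or the protocol says otherwise. Whether the odd and even numbering in E1 is compatible with concealment is a separate question.

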The research coordinator will then complete page one of the Ketamine Data Form. This includes the participant's medical history, including a history of drug abuse, or prior narcotic use, a description of the injury, prior medications given to the subject for this injury either by EMS or in the emergency department, baseline vital signs (prior to study drug administration) and the time of study drug administration. Page 2 includes the baseline (pre study drug administration) visual analog pain scale that the participant will complete.

MEDICATION ADMINISTRATION

If the participant has not yet had an IV placed, one will be placed by the nurse caring for the participant at this time. Study drug will then be administered.

VITAL SIGN COLLECTION

The participant's heart rate, blood pressure, respiratory rate and oxygenation saturation (by pulse oximetry) will be collected every 5 minutes for the first 30 minutes, and every 10 minutes

for the next 30 minutes. The study will terminate at the end of 60 minutes and a final set of vital signs will be recorded at that point on Page 3 of the Ketamine Data Form.

REEVALUATION & EXIT SURVEY

The participant will be asked to complete repeat visual analog pain scales at 15, 30, and 60 minutes following study drug administration. The VAS will be administered by a second study coordinator, who has been blinded to the vital sign information, since blood pressure response may allow unblinding to occur. The participant will not have access to their original score for comparison. The study coordinator will then complete the post treatment survey on Page 5. The participant will continue to receive standard care by the emergency department physicians and nurses to ensure adequate relief of pain, appropriate treatment of the underlying pathology, hemodynamic and neuropsychiatric stability, and appropriate diagnostic evaluation, disposition, and follow-up. Any adverse events that occur during the continued treatment of the participant until either admission or discharge will be recorded.

RESCUE MEDICATION

Subjects that do not obtain adequate pain relief within 15 minutes of study drug administration will be offered rescue medication with intravenous morphine sulphate at the same weight-based dose (0.01mg/kg; maximum 10 mg)

TREATMENT OF ADVERSE EVENTS AND SERIOUS ADVERSE EVENTS

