If five or more serious adverse events (SAE's) occur, we will have an institutional Data and Safety Monitoring Board perform an interim analysis to determine if there is a safety issue.

i Independent expert to monitor

We will perform an interim analysis on the AE's after every 10 patients. If we identify five or more SAE's, we will suspend the study until we have an institutional Data and Safety Monitoring Board perform an interim analysis to determine if there is a safety issue.

ii Institutional Data and Safety Monitoring Board

We will assign 3 independent experts to an institutional DSMB.

iii Independent Data and Safety Monitoring Board

We do not plan to have an independent DSMB

5.c Definitions of Adverse Events

Any untoward medical occurrence (signs, symptoms, lab abnormalities) associated with the use of study drug, whether or not considered drug related.

Serious Adverse Events (SAE's):

Any Adverse Event that in the opinion of the Investigator or Sponsor results in:

Death or is life-threatening (immediate risk of death)

Hospitalization or prolongation of existing hospitalization

Persistent or significant incapacity or substantial disruption of the ability to conduct normal life functions (aka disability)

In addition, we have defined the following vital sign and behavioral abnormalities as SAE's:

Apnea: period of no respirations for greater than 20 seconds

Hypotension: systolic blood pressure < 90 mmHg

Hypertension: systolic blood pressure > 180 mmHg

Laryngospasm: Reflexive closure of the vocal cords that results in inability to ventilate.

Emergence Reaction: Anxiety, agitation, disorientation

Respiratory depression: respiratory rate < 8 breaths/min or sats < 92%

Bradycardia: Heart rate < 50 bpm

5.d Classification of Events

i Relationship

We will review each adverse event to see if it is associated with study drug.

The relationship of the AE to study drug will be based on temporal association, and other clinical information such as concomitant medications, pre-existing conditions, and the natural history of the disease process.

Investigator causality assessment (relationship of AE to study drug) will be categorized as: 1) Probably related 2) Possibly related 3) Unlikely related and 4) Not related.

ii Severity

Severity of the AE will be documented using the FDA categories of 1) mild, 2) moderate, 3) severe, and 4) potentially life threatening.

Expectedness

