Based on past research, we believe adverse events will be rare and severe events are unlikely to occur.

5.e Data Collection Procedures for Adverse Events

The research coordinator will write down all adverse events on the data form in the designated spot. They will also report the events to the treating team.

5.f Reporting Procedures

The research coordinator will report all adverse events to the principal investigator (PI) investigator during the study. The PI will determine severity and causality. The PI will keep track of adverse events to determine if the study needs to be stopped.

5.g Adverse Event Reporting Period

This is an acute treatment trial, with a duration of one hour following study drug administration. However, any AEs that occur at any time during the entire ED stay of the study participant will be reported.

Post-study Adverse Event

The duration of the drugs used in this study will not exceed the time the participant is monitored.

F6 Study Outcome Measurements and Ascertainment

Study outcomes involve change in participants' pain as measured by the VAS, significant changes in any vital signs collected, a list of adverse events that the participant experienced, as well as questions included in the data form assessing whether the participant would consider using the drug given to them for pain relief in the future.

G Statistical Plan

G1 Sample Size Determination and Power

Sample size for this study is based on limited funding and will serve as a pilot study looking for trends in the efficacy of morphine and ketamine to treat pain as well physiologic effects and adverse events. If the results appear promising, further funding will be requested and a full power analysis will be performed.

G2 Interim Monitoring and Early Stopping

All adverse events will be promptly reviewed by the primary research team following the participant's completion of the study. Any adverse event directly linked to administration of either ketamine or morphine that results in permanent disability or death will result in the cessation of the entire study. After every 10 patients are enrolled, adverse event information will be reviewed by an independent expert. If there is a high frequency of

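### Symptom adverse events are recorded by the role that also monitors vital signs, which E1 concedes may unblind, so their recording can differ by arm

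*SAP*

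**What the plan says.** Section E1 (Reevaluation & Exit Survey) has the VAS administered by a second study coordinator "who has been blinded to the vital sign information, since blood pressure response may allow unblinding to occur". Section 2.g shows why blood pressure is informative. For one arm, "Patients exposed to ketamine will be at risk for hypertension, dysphoria and in rare cases laryngospasm and emergence reaction". For the other, "Patients exposed to morphine will be at risk for hypotension, respiratory depression, altered mental status and possible allergic reaction".

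Section 2.n assigns monitoring to one role: "The research coordinator will monitor the participant's vital signs, pain relief, and any side effects during the duration of the study". Section 5.e then says "The research coordinator will write down all adverse events on the data form in the designated spot". Under 5.f the principal investigator judges severity and causality on what that role reports.

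F6 lists among the study outcomes "a list of adverse events that the participant experienced". Section 5.c adds one symptom-based entry to the SAE list, in these words only: "Emergence Reaction: Anxiety, agitation, disorientation". It gives no scale, threshold or grading.

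**The concern.** The plan accepts that someone who sees the blood pressure may work out the treatment, and it acts on this for pain. Yet the participant completes the VAS personally. Whether a patient with a fresh fracture is anxious, agitated, disoriented, dysphoric or nauseated depends far more on who is looking and how hard. That outcome is left with the role that sees the vital signs.

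A recorder who has seen the pressure rise could look harder for the reactions that 2.g lists for ketamine. Alternatively, the recorder could put the same disorientation down to altered mental status, which 2.g lists for morphine. Either way, two arms with the same true symptom rate could show different recorded rates. According to G1 the trial is a pilot that looks for trends, adverse events included, and decides whether to seek further funding. A trend produced by recording could feed that decision.

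**Working it through.** **Step 1. Who does what.** The plan states no figure on this point, so the main check sets the assignments side by side.

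| Task | Section | Role | Kept from vital signs? |
|---|---|---|---|
| VAS at 15, 30 and 60 minutes | E1 | second coordinator | yes |
| Monitoring vital signs | 2.n | research coordinator | no |
| Monitoring side effects | 2.n | research coordinator | no |
| Writing down all adverse events | 5.e | research coordinator | not stated |
| Post-treatment survey, page 5 | E1 | study coordinator, first or second not stated | unclear |

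The shield appears in the first row only. The general statement in the SAP that all study personnel are blinded does not settle the matter, because E1 adds the second coordinator on the ground "since blood pressure response may allow unblinding to occur".

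**Step 2. Which events are exposed.** SAEs in 5.c that are set by a vital-sign cut-off leave little to judgement. The exposed events are nausea (F5), dysphoria (2.g) and emergence reaction (F5, 5.c). Of these, only emergence reaction is in the added SAE list.

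**Step 3. Illustration of size.** The only input from the document is 20 participants per arm (2.f). The true rate p, equal in both arms, and the recording probabilities s1 and s2 are assumptions.

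Expected recorded count in an arm = 20 × p × s. At p = 0.20:
- s = 0.90: 20 × 0.20 × 0.90 = 3.6
- s = 0.70: 20 × 0.20 × 0.70 = 2.8
- s = 0.50: 20 × 0.20 × 0.50 = 2.0

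The chance that the first arm shows at least 3 more recorded events is P(X − Y ≥ 3), with X ~ Bin(20, p·s1) and Y ~ Bin(20, p·s2), computed exactly:

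| p | s1, s2 | Expected counts | P(X − Y ≥ 3) |
|---|---|---|---|
| 0.10 | 0.90, 0.90 | 1.8, 1.8 | 8.0% |
| 0.10 | 0.90, 0.70 | 1.8, 1.4 | 10.6% |
| 0.10 | 0.90, 0.50 | 1.8, 1.0 | 13.9% |
| 0.20 | 0.90, 0.90 | 3.6, 3.6 | 15.0% |
| 0.20 | 0.90, 0.70 | 3.6, 2.8 | 22.8% |
| 0.20 | 0.90, 0.50 | 3.6, 2.0 | 33.5% |
| 0.30 | 0.90, 0.90 | 5.4, 5.4 | 18.6% |
| 0.30 | 0.90, 0.70 | 5.4, 4.2 | 31.4% |
| 0.30 | 0.90, 0.50 | 5.4, 3.0 | 48.4% |

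The expected gap is small in patients: 3.6 − 2.8 = 0.8 and 3.6 − 2.0 = 1.6 at p = 0.20. It still raises the chance of an apparent trend.

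**Step 4. The five-SAE trigger.** Section 5.b counts SAEs without regard to arm. With p = 0.20 and recording of 0.90 and 0.70, the expected total is 3.6 + 2.8 = 6.4. With 0.80 in both arms it is 2 × 20 × 0.20 × 0.80 = 6.4. The expected total depends on how much is recorded overall, not on the difference between arms.

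**The case against.** **The roles are partly generic.** The vital-sign schedules in E1 and F2 are in the passive and name no recorder. Section 2.n also gives the research coordinator pain relief, although E1 hands the VAS to a second person, so the title may be a label for the team. A reader might infer that the person writing down adverse events also takes the readings every 5 minutes; the document does not say that. What stands is that 2.n and 5.e place both tasks in one role and no section separates them.

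**The data form is not shown.** It may already hold a symptom checklist, and the second coordinator may already complete the page 5 survey. That would lower the risk, but neither 5.e nor 2.n says so.

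**A symptom checklist could do harm.** Asked at 15 and 30 minutes, it could cue the VAS administrator to the arm, just as blood pressure would. It would also miss events between contacts and after 60 minutes, although 5.a requires continuous monitoring and 5.g covers the whole ED stay. This stands, and it governs the timing and scope of the fix.

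**The size is assumed, and chance is large here.** At a 20% true rate, a gap of 3 or more in a named direction arises 15.0% of the time with equal recording. F6 specifies no test. This limits the weight of the point but does not make the recording neutral.

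**Conclusion.** The point holds as a design weakness: the plan identifies a route to unblinding, closes it for pain, and leaves it open for the symptom events in F6 that depend most on the recorder. It rests on reading the research coordinator in 2.n and 5.e as one role, and on E1's own premise that blood pressure may unblind.

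Three stronger readings are not supported:
- **That symptom events in general enter the SAE count.** Among those at issue, 5.c adds only emergence reaction. Nausea is not listed, and dysphoria appears only as a risk in 2.g.
- **That the arm difference distorts the five-SAE trigger.** The trigger is not arm-specific, as step 4 shows.
- **That the bias must run against ketamine.** 2.g lists mental effects for both drugs, and the document gives no basis for size or direction.

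Under the assumptions in step 3 (true rates of 10% to 30%, recording of 90% against 70% or 50%), the chance of at least 3 more recorded events in the better-recorded arm is 10.6% to 48.4%, against 8.0% to 18.6% with equal recording at 90%. These are illustrations, not estimates for this trial.

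**What to change.** Add to 5.e, in substance: *Immediately after the 60-minute VAS is completed, the second coordinator, who remains blinded to vital signs, asks and records a fixed checklist of symptoms over the full hour (nausea, vomiting, anxiety, agitation, disorientation, dysphoria). The comparison of symptom events between arms uses this checklist.*

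Asking after the last VAS means that the answers cannot influence any pain score. The first coordinator continues to record all events throughout, including vital-sign events and those after 60 minutes. Reporting to the treating team and the SAE count do not change. The same edit should state which coordinator completes the page 5 survey.

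The cost is a short addition to 5.e, a checklist on the form and about a minute at one existing contact, with no new staff. The downsides are some reliance on recall over the hour and that symptoms may themselves hint at the arm, so the bias is reduced rather than removed. Section 2.j foresees that some follow-up VAS scores will be missed. The checklist may be missed in the same participants, so the number without it should be reported by arm.
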